## **5.5 EXPLORATORY ENDPOINTS ANALYSIS**

### **5.5.1.1 Intracranial Objective Response Rate - iRANO**

Intracranial ORR is defined as the proportion of patients with either a CR or PR in their intracranial disease as assessed by the investigator according to iRANO criteria based on two consecutive assessments  $\geq 4$  weeks apart.

Intracranial ORR will be analyzed using the same methods as described in Section [5.3.2](#).

### **5.5.1.2 Intracranial, Extracranial and Overall Objective Response Rate – Immune-Modified RECIST**

ORR in intracranial, extracranial and overall disease are defined as described in Sections [5.4.2.1](#), [5.4.2.2](#), and [5.4.2.3](#) but determined by investigator according to immune-modified RECIST with modified measurability definition for intracranial lesions ( $\geq 0.5$  cm by MRI) and allowing up to five intracranial target lesions.

Intracranial, extracranial, and overall ORR will be analyzed using the same methods as described in Section [5.3.2](#).

### **5.5.1.3 Intracranial, Extracranial, and Overall Progression-Free Survival – Immune-Modified RECIST**

Intracranial, extracranial, and overall PFS are defined as described in Section [5.4.2.4](#) but determined by the investigator according to immune-modified RECIST.

Intracranial, extracranial, and overall PFS will be analyzed using the same methods as described in Section [5.4.2.4](#).

### **5.5.1.4 Intracranial, Extracranial, and Overall Duration of Response – Immune-Modified RECIST**

Intracranial, extracranial, and overall DOR are defined as described in Section [5.4.2.5](#) but determined by the investigator according to immune-modified RECIST.

Intracranial, extracranial, and overall DOR will be analyzed using the same methods as described in Section [5.4.2.5](#).

### **5.5.1.5 Radiotherapy-Assisted Progression-Free Survival – RECIST**

Radiotherapy-assisted intracranial PFS is defined as the time from study treatment initiation to the first occurrence of disease progression or death from any cause, whichever occurs first, as determined by the investigator according to RECIST v1.1 modified by excluding  $\leq 3$  lesions that can be treated by SRT from the sum of largest diameters from baseline onwards. The censoring method is the same as the one described for PFS analysis in Section [5.4.2.4](#).

For the purpose of the analysis of radiotherapy-assisted PFS, the disease status will be derived by removing the lesions treated by SRT (3 maximum) from sum of longest diameters (SLD), from baseline onwards.

Radiotherapy-assisted PFS will be analyzed using the same methods as described in Section [5.4.2.4](#).

#### **5.5.1.6 Timing of Increase or Change in Corticosteroid Use**

The analysis of timing of increase in corticosteroid use during treatment will be based on the safety population.

A summary table of the status of corticosteroids (None / Stable or decreased / Increased) during treatment, as collected in the 'iRANO Response assessment' electronic Case Report Form (eCRF) page will be provided by visit.

The time to increase in corticosteroid use is defined as the time from study treatment initiation to the first increase in corticosteroid use during treatment. Data for patients who have not experienced any increase in corticosteroid use during treatment, at the time of analysis data cutoff, will be censored at the last iRANO response assessment date during treatment. Timing of increase or change in corticosteroid use will be analyzed using the same methods as described in Section [5.4.2.4](#).

For patients on corticosteroids for disease control at study entry, the number of patients with a change in the corticosteroid use (increase/decrease/off) will be summarized descriptively based on the medication case report form (CRF) page if applicable.

#### **5.5.1.7 Time to Subsequent Intracranial and Systemic Anti-Cancer Treatment**

The analysis of time to subsequent intracranial and systemic anti-cancer treatment will be based on the safety population.

Time from study treatment initiation to subsequent intracranial and systemic anti-cancer treatment is defined as the time from study treatment initiation to the date of first administration of subsequent systemic anti-cancer therapy. Data for patients who have not received any subsequent anti-cancer treatment at the time of analysis data cutoff will be censored at the time of study termination or at the cutoff data, whichever occurs first.

Time to subsequent intracranial and systemic anti-cancer treatment will be analyzed using the same methods as described in Section [5.4.2.4](#).

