3.3.5 Rationale for Treatment beyond Disease Progression per RECIST v1.1

Patients in either study cohort may continue treatment beyond disease progression per RECIST v1.1 for two reasons: possible pseudoprogression due to immunotherapy, or disease progression is limited to ≤ 3 intracranial lesions that may be controlled by SRT.

In studies of immunotherapeutic agents, complete response (CR), PR and stable disease (SD) have each been shown to occur after radiographic evidence of an apparent increase in tumour burden. This initial increase in tumour burden caused by immune-cell infiltration in the setting of a T cell response has been termed pseudoprogression ([Hales et al. 2010](#)). In single agent atezolizumab studies (Study PCD4989g – see Atezolizumab Investigator's Brochure), evidence of tumour growth followed by a response was observed in several tumour types. In addition, in some responding patients with radiographic evidence of progression, biopsies of new lesions or areas of new growth in existing lesions revealed infiltrating immune cells and no viable cancer cells. Because of the potential for a response after pseudoprogression, this study will allow treatment in either cohort to continue after apparent radiographic progression per RECIST v1.1, provided the benefit-risk ratio is judged to be favourable (see criteria in Section [3.1](#)).

The blood brain barrier limits drug delivery to intracranial disease sites ([Agarwala et al. 2000](#)). A probable result of this sequestration is that, while disease outcomes have improved with the introduction of new systemic agents (see Section [1.1](#)), intracranial disease progression despite stable or responding extracranial disease has become more common ([Soliman et al. 2015](#)). Though randomized studies evaluating systemic treatment with SRT are limited, the practice of managing brain lesions with SRT in patients whose extracranial disease is controlled by systemic treatment has become a common clinical practice. The value of this approach has been supported by multiple retrospective analyses in melanoma patients receiving SRT with immunotherapy and/or targeted agents ([Anderson et al. 2017](#); [Choong et al. 2017](#), [Ahmed et al. 2016](#); [Mathew et al. 2013](#); [Knisely et al. 2012](#)).

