6.4.3 Exploratory Efficacy Endpoints

The exploratory efficacy endpoints are listed in [Table 1](#) and are as follows:

- Intracranial ORR defined as the proportion of patients with either a CR or PR in their intracranial disease as assessed by the investigator according to iRANO criteria based on two consecutive assessments ≥ 4 weeks apart.
- Objective response rate in intracranial, extracranial and overall disease as determined by investigator according to immune-modified RECIST with modified measurability definition for intracranial lesions (≥ 0.5 cm by MRI) and allowing up to five intracranial target lesions.
- Intracranial, extracranial and overall PFS is determined by the investigator according to immune-modified RECIST.

- Intracranial, extracranial and overall DOR is determined by the investigator according to immune-modified RECIST
Objective response, PFS and DOR, as determined by the investigator according to immune modified RECIST, will be analysed using the same methods as described in Section 6.4.2.
- Radiotherapy-assisted PFS defined as time from study treatment initiation to the first occurrence of disease progression or death from any cause, whichever occurs first, as determined by the investigator according to RECIST v1.1 modified by excluding ≤ 3 lesions that can be treated by SRT from the sum of largest diameters from baseline onwards
- Timing of increase or change in corticosteroid use during treatment will be based on corticosteroid used for symptomatic control as indicated in the eCRF
- Time from study treatment initiation to subsequent intracranial and systemic anti-cancer treatment
- Change from baseline scores over time in treatment/disease-related symptoms as evaluated by the EORTC QLQ-C30 and QLQ-BN20 questionnaires will be summarized descriptively including the mean change from baseline of linear-transformed scores for all subscales of the EORTC QLQ-C30 and QLQ-BN20 according to the EORTC scoring manual guideline at each assessment time point for each cohort, including progression, treatment discontinuation and post-study discontinuation. The mean (and 95% CI) and median of the absolute scores and the change from baseline will be reported for interval and continuous variables. Only patients with a non-missing baseline assessment and at least one non-missing post-baseline assessment will be included in PRO analyses.

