Patients will attend a Study Treatment Discontinuation Visit within  $28 \pm 7$  days of their last study treatment dose. All AEs will be reported until 30 days after the last study treatment dose. After the Study Treatment Discontinuation Visit, patients who have not yet progressed will be followed every 8 or 12 weeks for disease status until disease progression has been confirmed, and all patients will be followed every three months for survival and new anti-cancer treatments.

Figure 1 presents an overview of the study design.

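### SAP 5.5.1.7 counts only systemic therapy as the event, although the protocol and the rest of the SAP define the endpoint to cover later intracranial treatment as well

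*SAP*

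**What the plan says.** Protocol 6.4.3 lists as an exploratory endpoint "Time from study treatment initiation to subsequent intracranial and systemic anti-cancer treatment", and SAP Table 1 repeats it. When assigning populations, Protocol 6 and SAP 5.1 also name intracranial treatment, joined to systemic by *or* and followed by *endpoints* in the plural.

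SAP 5.5.1.7 carries the full name in its heading and in its population sentence: "The analysis of time to subsequent intracranial and systemic anti-cancer treatment will be based on the safety population". Its event date, however, is "the date of first administration of subsequent systemic anti-cancer therapy". No date is given for intracranial treatment. The patients to be censored are described more widely than the event: "Data for patients who have not received any subsequent anti-cancer treatment at the time of analysis data cutoff". They "will be censored at the time of study termination or at the cutoff data, whichever occurs first". The analysis is the Kaplan-Meier approach of SAP 5.4.2.4.

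SAP 5.7.2 summarises on-study and follow-up radiotherapy and surgery by cohort, descriptively. SAP Appendix 1 declares two departures from the protocol, both about patient-reported time to deterioration. The SAP's amendment rationale has no entry for 5.5.1.7.

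**The concern.** The operational definition does not measure the endpoint it is named for. The part left out is the part specific to this population: Protocol 1.1 describes surgery, whole-brain radiotherapy and stereotactic radiotherapy as mainstays for melanoma brain metastases, and Protocol 3.3.5 says that "the practice of managing brain lesions with SRT in patients whose extracranial disease is controlled by systemic treatment has become a common clinical practice". A patient may well have local brain treatment before, or instead of, a new systemic drug. If 5.5.1.7 is programmed as written, the reported time will run longer than the time to any further treatment, and a reader of the endpoint's title would not know why.

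There is a separate weakness in the censoring rule. It does not say what happens to patients who are lost, withdraw or die before the cutoff without further treatment.

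**Working it through.** **Step 1. Apply the rules of SAP 5.5.1.7 to each kind of patient.**

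| Later treatment | Event rule | Censoring rule | Result |
|---|---|---|---|
| Systemic first or only | Event at that date | Not applicable | As intended |
| Local brain treatment first, systemic later | Event at the systemic date | Not applicable | Dated late |
| Local brain treatment only | No event | Not covered, because the patient has had an anti-cancer treatment | No rule applies |
| None, followed to cutoff | No event | Cutoff | As intended |
| None, lost or withdrawn | No event | Study termination or cutoff | Depends on an undefined term |
| None, died | No event | Not addressed separately | Depends on an unstated estimand |

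Rows 2 and 3 follow from the event sentence alone. The censoring date plays no part in them.

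The SAP cites protocol Version 4.0, while the protocol at hand is Version 5.0. The mismatch does not turn on that, because SAP Table 1 carries the same endpoint wording.

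**Step 2. Size.** The documents state no figure for this endpoint, so there is nothing to reproduce. What follows is illustration only, and every rate is an assumption: independent exponential times, median 9 months to systemic therapy, 12, 24 or 48 months to local brain treatment, and 12 or 18 months to death.

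With death censored at death, the systemic-only median is 9.0 months. The median to the earlier of the two treatments is 1/(1/9 + 1/m), where m is the local median:
- m = 12: 108/21 = 5.1 months
- m = 24: 216/33 = 6.5 months
- m = 48: 432/57 = 7.6 months

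With deaths kept at risk until cutoff, the median is −ln(1 − 0.5(h + d)/h)/(h + d). Here h is the event hazard and d the death hazard, each ln 2 divided by its median (hazards add when either treatment counts).

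| Death median | Systemic only | Either, m = 12 | Either, m = 24 | Either, m = 48 |
|---|---|---|---|---|
| 12 months | 15.4 | 6.5 | 9.1 | 11.3 |
| 18 months | 12.0 | 5.9 | 7.9 | 9.5 |

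So the systemic-only event lengthens the median whichever way death is handled.

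The share with local treatment first is about (1/m)/(1/9 + 1/m + 1/k), with k the death median. It runs from 0.0208/0.2153 = 10% (m = 48, k = 12) to 0.0833/0.25 = 33% (m = 12, k = 18), about 6 to 20 of roughly 60 Cohort 2 patients. A simulation at the same rates, with cutoff between 24 and 36 months, gave 4% to 14% (about 3 to 8 of 60) with local treatment only.

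**Step 3. Handling of death, on the same assumed rates.** The true proportion starting systemic therapy by 24 months is h/(h + d) × (1 − exp(−24(h + d))).
- Death median 12: 0.571 × (1 − 0.039) = 54.9%
- Death median 18: 0.667 × (1 − 0.0625) = 62.5%

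Keeping untreated deaths at risk to an administrative cutoff estimates exactly this quantity. Censoring at death gives 1 − 2^(−24/9) = 84.3%, which overstates how many patients go on to further therapy.

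**The case against.** The strongest reply is that this is a drafting slip. The heading, SAP Table 1, SAP 5.1 and the description of the censored group all keep intracranial treatment in scope, so a programmer might restore it. Brain-directed treatment also remains visible in SAP 5.7.2, and intracranial PFS and radiotherapy-assisted PFS cover intracranial failure. The slip reading may be right about intent. But the event sentence is the one that would be programmed, and nothing in the SAP overrides it. The descriptive summaries give no time to event. The plural *endpoints* in SAP 5.1 also leaves open whether one combined endpoint or two were meant, which is a reason to report each.

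A reader might infer more than the documents support:
- *That the censoring rule is why brain treatment is missed.* It is not; the event definition alone does that.
- *That a patient who dies untreated necessarily adds spurious treatment-free time up to the cutoff, and that censoring at death is the cure.* The SAP states no estimand, and Step 3 shows that holding deaths at risk to an administrative cutoff recovers the crude incidence, while censoring at death does not.
- *That study termination must mean the end of the whole study.* SAP 5.5.1.7 does not define it. Protocol 4.5.11 lists termination by the sponsor separately from death and loss to follow-up, which favours the study-level reading, but the choice between that date and the cutoff would be natural for a patient's own end of study.

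**Conclusion.** The point stands on the event definition. SAP 5.5.1.7 gives a rule that contradicts the endpoint's name in Protocol 6.4.3, SAP Table 1 and SAP 5.1. The change is undeclared, and patients treated only locally are left without any rule. The error runs towards longer reported times. Its size cannot be drawn from the documents; the medians and shares above rest wholly on assumed rates and show direction and plausible scale only.

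On censoring, the finding is narrower: the rule is under-specified for loss to follow-up, withdrawal and death. Keeping lost or withdrawn patients at risk to the cutoff would assume they had no treatment after contact ended, which nobody observed.

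The endpoint is exploratory in an entirely descriptive study. The primary endpoint and the sample size are unaffected.

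**What to change.** In SAP 5.5.1.7:
- Define three event dates: first subsequent intracranial treatment (radiotherapy or surgery), first subsequent systemic treatment, and the earlier of the two. Report each.
- State whether SRT given during continued study treatment, which Protocol 4.3.2.3 permits, counts as subsequent for this analysis.
- Make the description of the censored group match each event definition.
- For patients lost or withdrawn, censor at the last contact with known treatment status, in place of study termination or cutoff.
- Treat death without subsequent treatment explicitly, either as a competing event with cumulative incidence or as part of a composite, and not as simple censoring at death.
- If a systemic-only endpoint is really intended, rename it and declare the change in Appendix 1.

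The cost is SAP wording and programming. Under SAP 1.2, "all patients will be followed every three months for survival and new anti-cancer treatments", and SAP 5.7.2 already plans to summarise follow-up radiotherapy and surgery. One thing to check first: the documents do not say whether the anatomical site of those later treatments is recorded, and the intracranial date depends on it.

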In a clinical trial of 146 patients with BRAF^{V600} mutation-positive disease (n=90 with no prior treatment for brain metastases, n=56 with prior treatment for brain metastases), MAPK pathway disruption via BRAF inhibition with vemurafenib (Zelboraf®) produced an intracranial ORR of 18% in both prior treated and untreated patient cohorts. Median OS was 9.6 months (range 0.6–34.5) in the prior treatment cohort and 8.9 months (range 0.7–34.3) in the cohort of patients who had not received prior treatment for brain metastases. Study treatment was reported as well tolerated (McArthur et al. 2017). In a study of dual MAPK pathway blockade with combined BRAF and MEK inhibition with dabrafenib (a BRAF inhibitor) and trametinib (a MEK inhibitor) in patients with BRAF^{V600} mutation-positive disease, intracranial responses were observed in 58% of the patients

Cobimetinib, atezolizumab, vemurafenib — F. Hoffmann-La Roche Ltd

32 / Protocol MO39136, Version 5.0

with asymptomatic disease and no prior treatment. Preliminary OS analyses in this patient subset found median survival ranging from approximately 10 to 24 months. No unexpected safety issues were observed ([Davies et al. 2017](#)).

These results suggest that immunotherapy and BRAF-MEK targeted approaches may provide systemic alternatives to established, but arguably inadequate, local methods for treating melanoma patients with intracranial disease.

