4.5.11 Post-treatment Survival

Post-treatment survival, in addition to PROs and anti-cancer treatments, will be collected via telephone calls and/or clinic visits every three months until death, loss to follow-up, or study termination by the Sponsor.

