4.6.2 Patient Discontinuation from Study

Patients have the right to voluntarily withdraw from the study at any time for any reason. In addition, the investigator has the right to withdraw a patient from the study at any time. Reasons for withdrawal from the study may include, but are not limited to, the following:

- Patient withdrawal of consent
- Patient non-compliance, defined as failure to comply with protocol requirements as determined by the investigator or Sponsor

- Study termination or site closure

Every effort should be made to obtain information on patients who withdraw from the study. The primary reason for withdrawal from the study should be documented on the appropriate eCRF. If a patient requests to be withdrawn from the study, this request must be documented in the source documents and signed by the investigator. Patients who withdraw from the study will not be replaced.

If a patient withdraws from the study, the study staff may use a public information source (e.g., county records) to obtain information about survival status.

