#### **5.4.2.4 Intracranial, Extracranial and Overall Progression-Free Survival – RECIST**

Intracranial, extracranial, and overall progression-free survival (PFS) are defined as the time from study treatment initiation to the first occurrence of disease progression, as

determined by the investigator according to RECIST v1.1, or death from any cause, whichever occurs first. Data for patients who have not experienced disease progression or death at the time of analysis data cutoff will be censored at the last evaluable tumor assessment date.

Kaplan-Meier methodology will be used to estimate median intracranial, extracranial, and overall PFS. Kaplan-Meier curves will be provided. The 95% CI of the median PFS will be constructed using the Brookmeyer and Crowley method (Brookmeyer and Crowley 1982).

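### SAP 5.5.1.7 leaves the handling of death and loss to follow-up undefined for time to subsequent therapy, and SAP 5.5.1.6 censors patients at treatment stop for time to steroid increase; neither Kaplan-Meier curve gives a dependable proportion.

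*SAP*

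**What the plan says.** In SAP 5.5.1.7 the endpoint is "defined as the time from study treatment initiation to the date of first administration of subsequent systemic anti-cancer therapy". Patients with no subsequent treatment are "censored at the time of study termination or at the cutoff data, whichever occurs first". Death is given no role: it is not an event, a competing event or a named censoring date. For the estimator, "Time to subsequent intracranial and systemic anti-cancer treatment will be analyzed using the same methods as described in Section" 5.4.2.4, and there "Kaplan-Meier methodology will be used to estimate median intracranial, extracranial, and overall PFS". In 5.4.2.4 death counts as an event; 5.5.1.7 borrows the method but has its own event definition, without death.

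Study termination is not defined in the SAP section. Protocol 4.5.11 collects survival and anti-cancer treatment "every three months until death, loss to follow-up, or study termination by the Sponsor", which sets it apart from death and loss. Protocol 4.6.2 gives "Study termination or site closure" as one reason why a patient may leave the study.

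In SAP 5.5.1.6 the event is the first increase in corticosteroid use while on treatment. Patients without one "will be censored at the last iRANO response assessment date during treatment", and the same Kaplan-Meier method is used.

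**The concern.** A patient who dies without further therapy can never receive it. A time-to-therapy analysis therefore has to say what happens to that patient, and also to one whose later treatment is unknown. Section 5.5.1.7 says neither, and its one censoring rule can be programmed in two ways that give different curves from the same data.

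In 5.5.1.6 the event can occur only during treatment, so stopping treatment rules it out. Censoring at the last on-treatment assessment treats those patients as though an on-treatment increase could still happen later.

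Deaths are expected in this disease. In the vemurafenib study cited in protocol section 1.1, "Median OS was 9.6 months (range 0.6–34.5) in the prior treatment cohort and 8.9 months" in patients without prior treatment for brain metastases. That shows only the scale of mortality: it is all-cause survival on another regimen, not a rate of death before further therapy.

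**Working it through.** The SAP states no figure for either endpoint, so there is none to reproduce. The check compares what each reading estimates with the true proportion.

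**Inputs.** From the documents: about 60 patients in Cohort 2; final cutoff 24 months after the last patient enters; study length about 48 months, hence an assumed 24-month accrual window. Assumed, because the documents give no such values: constant hazards; median time to next therapy 9 to 18 months; median time to death without therapy 12 to 48 months; median time to loss 60 months; for steroids, medians of 18 months to an increase and 5.5 months to treatment stop.

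**Formulas.** With hazards a (event) and b (competing event), each ln 2 divided by its median:
- true cumulative incidence = a/(a+b) × (1 − exp(−(a+b)t));
- one minus Kaplan-Meier with the competing event censored when it occurs = 1 − exp(−a·t).

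**5.5.1.7, patient-level reading (untreated deaths censored at death).** With medians of 12 months (therapy) and 24 months (death first), a/(a+b) = 2/3 and a+b = ln 2/8. At 24 months the true value is 2/3 × (1 − 1/8) = 58.3%, and one minus Kaplan-Meier is 1 − 1/4 = 75.0%. At 12 months the values are 43.1% and 50.0%. Differences over the grid, in percentage points:

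| Therapy median | Death-first median | 12 months | 24 months |
|---|---|---|---|
| 9 | 12 | 14.5 | 29.4 |
| 9 | 48 | 4.2 | 9.4 |
| 12 | 12 | 12.5 | 28.1 |
| 12 | 24 | 6.9 | 16.7 |
| 12 | 48 | 3.6 | 9.1 |
| 18 | 12 | 9.6 | 24.3 |
| 18 | 48 | 2.8 | 8.0 |

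The median moves too. In the 12/24 case Kaplan-Meier gives 12 months, while 2/3 × (1 − 2^(−t/8)) = 0.5 gives t = 16 months. In the 12/12 case the cumulative incidence is 0.5 × (1 − 2^(−t/6)), which never reaches 50%, so no median exists.

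**5.5.1.7, sponsor-level reading (untreated deaths held to the administrative date).** In 3,000 simulated trials of 60 patients with the final cutoff, one minus Kaplan-Meier averaged 58.2% at 24 months against the true 58.3%, so deaths cause no overstatement. Lost patients are also held at risk, however, and their later therapy is never seen. With a loss median of 60 months the simulated estimate is 53.4% against 58.3%. A closed form agrees: with c = ln 2/60, a/(a+b+c) = 0.588 and exp(−24(a+b+c)) = 2^(−3.4) = 0.095, giving 0.588 × 0.905 = 53.3%. In this scenario c/(a+b+c) × 0.905 = 10.7% of patients are lost before therapy or death by 24 months.

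**5.5.1.6.** With a = ln 2/18 and b = ln 2/5.5, at 12 months one minus Kaplan-Meier is 1 − exp(−0.462) = 37.0%. The true proportion with an on-treatment increase is 0.234 × (1 − exp(−1.974)) = 20.2%. This is one illustrative scenario.

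**Scale.** With 60 patients and complete follow-up, the standard error at 58.3% is √(0.583 × 0.417/60) = 6.4 points. The 16.7-point gap is 2.6 standard errors; the 4.9-point downward gap (58.3 − 53.4) is 0.8. Many patients will lack 24 months of follow-up at the primary analysis, so 24-month comparisons belong to the final one.

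**The case against.** The strongest objection is that 5.5.1.7 does not censor at death at all. The protocol treats termination by the sponsor as separate from death, and SAP 5.2 uses a different term, study discontinuation, for individual patients. On that usage untreated deaths stay in the risk set and the curve equals the cumulative incidence. This stands, and it defeats a reading that a reader might otherwise adopt: that the plan as written overstates the proportion going on to further therapy. The documents do not fix that direction. Nor do they settle on the sponsor-level reading. Barring early closure, termination by the sponsor would not precede a primary cutoff six months after the last patient enters, so the whichever-is-first clause would do nothing there. Even on the sponsor-level reading, patients who are lost or withdraw are miscounted.

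Second, the hazards are not in the documents. That is correct: the sizes show sensitivity and do not predict this trial. It also cannot be said from the documents that death before further therapy will be common.

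Third, 5.5.1.7 plans a curve and a median, not a proportion, and SAP 5.7.2 separately tabulates follow-up cancer therapy. But the curve is read as a proportion over time and the median moves as shown. A crude count over unequal follow-up does not replace either.

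Fourth, the steroid endpoint is explicitly an on-treatment one, so censoring at treatment stop might be a deliberate choice of target. That curve would describe increases had treatment continued, assuming that stopping is unrelated to steroid need. The SAP does not state that target, and the curve still overstates the proportion of patients who have an increase during treatment.

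**Conclusion.** The point holds in conditional form. For 5.5.1.7, death has no stated role and the censoring term is undefined. The patient-level reading overstates, by 8 to 29 points at 24 months over the assumed medians. The sponsor-level reading handles deaths correctly but is too low whenever patients are lost or withdraw, by about 5 points in the one scenario run. An unconditional claim of overstatement is not supported for this section. For 5.5.1.6 the overstatement does not depend on that term, because the censoring date is explicitly on treatment; its size (37.0% against 20.2%) comes from a single assumed scenario.

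Both endpoints are exploratory and the study tests no hypothesis, so the priority is low. The primary endpoint is unaffected.

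**What to change.** - **SAP 5.5.1.7:** report the cumulative incidence of first subsequent therapy with death as a competing event. Censor patients who are alive and untreated at the earlier of last contact and the data cutoff. Drop the term study termination or define it.
- **SAP 5.5.1.6:** report the cumulative incidence of an on-treatment steroid increase with treatment discontinuation and death as competing events. Patients still on treatment at the cutoff stay censored at their last assessment.

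A composite of subsequent therapy or death would also resolve 5.5.1.7, but it changes the endpoint in protocol Table 1, so cumulative incidence is the smaller change.

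The cost is a few sentences in the SAP and a standard cumulative-incidence routine. Survival and later anti-cancer treatment are already collected every three months (protocol 4.5.11) and treatment discontinuation is recorded (protocol 4.6.1), so no new data are needed.
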